### **3.10.1 Screen failures**

Patients who fail to meet the inclusion or meet the exclusion criteria will be defined as screening failures. The PI will maintain a Screening Failure List which includes screen failures in the Investigator's Study File. The list will document the subject number, subject initials, demographics and the reason(s) for excluding the patient from the study. It will be used to determine systematic bias in selection of patients for entry into the study.

### **3.10.2 Withdrawal of the informed consent**

Subjects are free to withdraw from the study at any time for any reason. Should a subject withdraw a consent, every effort will be made to complete and report the observations as thoroughly as possible.

### **3.11 Discontinuation of the study**

The Sponsor or PI may discontinue the study prematurely at any time due to the following reasons:

- the safety of the participants is doubtful or at risk,
- alterations in accepted clinical practice that make the continuation of a clinical trial unwise,
- early evidence of benefit or harm of the experimental intervention
- insufficient participant recruitment.

Clinical Study Protocol  
Drug Substance ticagrelor  
Study Code KB/112/2016  
Edition I  
Date

#### **4. STUDY PLAN AND TIMING OF PROCEDURES**

Visit	1	2	3	4	5	No follow-up	For details see Protocol Section
Visit window							
Day -1 to 0 for Visit 1							
±1 day for Visit 2							
±3 days for Visit 3							
±5 days for Visit 4							
± 6 months for Visit 5							
Week		0	1			24	
Day	-	0	1	3	5	168	
Written informed consent	X						
Demographics	X						
Physical examination, height, and weight	X		X	X	X	X	

Visit	1	2	3	4	5	No follow-up	For details see Protocol Section
Visit window							
Day -1 to 0 for Visit 1							
±1 day for Visit 2							
±3 days for Visit 3							
±5 days for Visit 4							
± 6 months for Visit 5							
Week		0	1			24	
Day	-	0	1	3	5	168	
Medical/surgical history	X						
Inclusion/exclusion criteria	X	X					
12-lead ECG	X		X	X	X	X	
Vital signs	X	X	X	X	X	X	
Randomisation to study treatment		X					
Treatment dispensed/returned		X				X	
Concomitant medication	X	X	X	X	X	X	
Adverse event review (AEs and SAEs)		X	X	X	X	X	

Visit	1	2	3	4	5	No follow-up	For details see Protocol Section
Visit window							
Day -1 to 0 for Visit 1							
±1 day for Visit 2							
±3 days for Visit 3							
±5 days for Visit 4							
± 6 months for Visit 5							
Week		0	1			24	
Day	-	0	1	3	5	168	
Blood samples for haematology and clinical chemistry	X			X		X	
Urinalysis	X			X		X	
Blood sampling for pharmacokinetics		n.a.	n.a.	n.a.	n.a.	n.a.	

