### 2.3 Safety objectives

Safety Objective:	Outcome Measure :
To evaluate the safety and tolerability of ticagrelor in relation to clopidogrel. To be reported descriptively.	

- Vital signs

- Abnormal values in blood tests ( haematology and clinical chemistry)

- Abnormal values or in urinalysis

- Abnormalities in 12-lead ECG

- AEs/ SAEs

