#### **6.1.1 Time period for collection of adverse events**

AE and SAE will be analyzed at each visit during index hospitalization and at the last visit at 6-months.

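### The in-hospital visit windows are nested, open on Day 0 or earlier and do not fit the day row, so the only early safety laboratory tests could fall before the randomised drug and still be in window

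*Combined protocol and SAP*

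**What the plan says.** The schedule table in section 4 lists these windows above the day row: "Day -1 to 0 for Visit 1", then ±"1 day for Visit 2", ±"3 days for Visit 3", ±"5 days for Visit 4" and ±"6 months for Visit 5". The same list stands in the header each time the table restarts. The day row has six entries (a dash for screening, then 0, 1, 3, 5 and 168), but the visits are numbered only 1 to 5. The sixth column is headed as no follow-up.

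"Randomisation to study treatment" and dispensing are marked in the Day 0 column. Physical examination, ECG, vital signs and adverse event review are marked at Days 1, 3, 5 and 168. Haematology, clinical chemistry and urinalysis are marked only at screening, Day 3 and Day 168.

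Section 2.3 sets the safety objective: "To evaluate the safety and tolerability of ticagrelor in relation to clopidogrel. To be reported descriptively". Its outcome measures include abnormal blood, urine and ECG findings. Section 6.1.1 adds: "AE and SAE will be analyzed at each visit during index hospitalization and at the last visit at 6-months".

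**The concern.** A visit window should keep an assessment near its planned time and on the intended side of the treatment start. These windows are as wide as, or wider than, the gaps between the visits they surround, and nothing makes them one-sided. I found no text elsewhere in the protocol that sets a minimum gap between visits or requires the in-hospital assessments to follow the first randomised dose.

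The exposed item is the Day 3 laboratory and urine set. Every subject has already had a clopidogrel loading dose before PCI. In the ticagrelor arm, a sample labelled Day 3 but taken before the randomised drug would therefore show the patient after clopidogrel loading only and could say nothing about ticagrelor. Such values would dilute the early description of the arms, and the next laboratory point is 6 months later.

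**Working it through.** The plan gives no resolved day ranges to reproduce, so the check is interval arithmetic: window = nominal day ± half-width. The half-widths for Visits 2, 3 and 4 are 1, 3 and 5 days, and the nominal days come from the day row, all in the section 4 table. Because five visit numbers cover six columns, two mappings have to be tried.

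*Mapping A, by matching the size of each window to a day.* Visit 1 covers screening and Day 0; Visits 2, 3 and 4 are Days 1, 3 and 5.

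*Mapping B, by printed column order.* Visits 2, 3 and 4 are Days 0, 1 and 3.

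| Visit | Mapping A | Mapping B |
|---|---|---|
| 2 | 1 ± 1 = Day 0 to 2 | 0 ± 1 = Day -1 to 1 |
| 3 | 3 ± 3 = Day 0 to 6 | 1 ± 3 = Day -2 to 4 |
| 4 | 5 ± 5 = Day 0 to 10 | 3 ± 5 = Day -2 to 8 |

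**Nesting.** A window lies wholly inside a later one when the gap between nominal days is no larger than the difference in half-widths.

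- Mapping A: Visits 2 and 3, 3 - 1 = 2 against 3 - 1 = 2; Visits 3 and 4, 5 - 3 = 2 against 5 - 3 = 2. Nested.
- Mapping B: Visits 2 and 3, 1 - 0 = 1 against 2; Visits 3 and 4, 3 - 1 = 2 against 2. Nested.

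The window widths, counted in calendar days, are 2×1 + 1 = 3, 2×3 + 1 = 7 and 2×5 + 1 = 11. Under either mapping Visit 2 therefore shares 3 days with Visit 3 and 3 with Visit 4, and Visit 3 shares 7 days with Visit 4. All three visits share Days 0 to 2 under A and Days -1 to 1 under B.

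**The Day 3 column.** Under A it is Visit 3, allowed from Day 0 to Day 6. Under B it is Visit 4, allowed from Day -2 to Day 8. Its earliest permitted time is thus the day of randomisation (A) or two days before it (B), against a nominal three days after it.

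**Likely origin.** The half-widths 1, 3, 5 days and 6 months coincide with the post-randomisation time points Day 1, 3, 5 and 168 (24 weeks × 7 = 168). Taken literally, the last entry gives 168 - 168 = Day 0 as the earliest 6-month visit, or 168 - 183 = Day -15 if six months is counted as 183 days (an assumption about month length). A list that lets the final visit fall on the day of randomisation was probably not meant as a list of windows.

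**The case against.** The strongest reply is that this is a clerical slip. Visit days were typed into a window field, staff will see patients on the nominal days, and nobody intends a pre-drug Day 3 sample. The first part is probably right. It explains the error without removing it, because the table is the only rule in the protocol for when these visits count as on schedule.

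Several limits also stand:

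- Mapping B is the weaker reading. It rests on printed column order in a table whose cells may have shifted on extraction, and it would give Day 5 the ±6-month window. Under mapping A no in-hospital window reaches before Day 0, so an assessment precedes the drug only if it is done earlier on Day 0 itself. It would then nearly repeat the screening tests already marked in the first column.
- Adverse events are less exposed than laboratory values. Section 6.1.3 records the date and time at which each event starts and stops, so events can be placed before or after treatment whatever the window. The question in section 6.2 refers back to the preceding visit and so presupposes visits in sequence.
- Safety is descriptive. Section 8.3.2 lists findings by treatment group and specifies no formal test between arms.

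A reader might infer that one examination could stand for several visits. Only a literal reading of the windows allows that: the table marks each visit's assessments separately. A reader might also infer that pre-drug visits would go unrecorded as deviations, but the protocol does not say how visit deviations are logged.

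**Conclusion.** The concern holds as an inconsistency in an operative scheduling table. Under either mapping the windows for Visits 2, 3 and 4 are nested and open on Day 0 or earlier. The Day 3 blood and urine tests, the only ones between randomisation and 6 months, may therefore be taken with no exposure to the randomised drug and still be within window. This does not depend on which mapping is right. That the ± values repeat the nominal days by mistake is an inference from their coincidence.

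The consequence is limited to a weaker descriptive early safety comparison, chiefly for ticagrelor. A reader might conclude that this comparison will be wholly pre-treatment. That would require pre-drug sampling in every subject, and nothing in the documents suggests it. Nor does the point reach the primary or secondary vesicle and aggregometry endpoints: section 5.7 times those samples separately, at 24 hours after clopidogrel loading, 48 hours after randomisation and 6 months. The change is worth making because it is cheap and protects the one early laboratory time point.

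**What to change.** Reconcile the visit numbers, day columns and windows in the section 4 table. Each day column should have its own window, the windows should not overlap, and assessments meant to be post-randomisation should not be able to fall before randomised treatment. The exact windows are for the sponsor to set. The 6-month entry should be checked in the same correction, since it appears to share the same cause.

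The cost is the correction of one table, with no added visits or tests. The small downside is that some visits may be logged as deviations that the present windows would have absorbed.

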#### **4.1 Enrolment/screening period**

6 months

#### **4.2 Treatment period**

6 months

#### **4.3 Follow-up period**

No follow-up period after the end of the study treatment.

### **5. STUDY ASSESSMENTS**

#### **5.1 Efficacy assessments**

The efficacy of ticagrelor will be assessed as a decrease in the concentration of EVs, in comparison with clopidogrel.

#### **5.2 Safety assessments**

##### **5.2.1 Laboratory safety assessments**

*Table x                      Laboratory Safety Variables*

---

Haematology/Haemostasis (whole blood)	Clinical Chemistry (serum or plasma)
B-Haemoglobin (Hb)	S/P-Creatinine
B-Leukocyte count	S/P-Aspartate transaminase (AST)
B-Platelet count	S/P-Alanine transaminase (ALT)
	S/P-Potassium
	S/P-Sodium
Urinalysis (dipstick)	
U-Hb/Erythrocytes/Blood	
U-Protein/Albumin	
U-Glucose	

---

## **5.2.2 Physical examination**

A comprehensive physical examination consisting of observation, percussion, palpation and auscultation will be conducted with state-of-the art questionnaire commonly used at 1st Chair and Department of Cardiology. The following will be examined: general appearance, skin (colour, hydration, oedema, scars, spots, haemorrhagic manifestations) , head and neck (eyes, ears, nose, mucous membranes, lymph nodes, thyroid gland), cardiovascular system (heart, carotid arteries, peripheral arteries), respiratory tract (chest, lungs), abdomen (peristaltic sounds, palpation of the abdominal organs including liver and spleen), neurological system (cerebral functions, cerebellum tests, motor and sensory nerves, cranial nerves, reflexes), musculoskeletal system (skeletal abnormalities, mobility).

## **5.2.3 ECG**

The ECG report will include heart rhythm, heart rate, heart axis, P wave, PR interval, QRS complex, ST segment, T wave, and QT interval.

### **5.2.3.1 Resting 12-lead ECG**

Resting 12-lead ECG will be performed using state-of-the-art ECG instrument available at 1st Chair and Department of Cardiology.

## **5.2.4 Vital signs**

The following vital signs will be examined: body temperature, respiratory rate, pulse rate, blood pressure.

### **5.2.4.1 Pulse and blood pressure**

Pulse and blood pressure will be measured at both arms during the first visit. If there is a difference less than 10 mmHg in systolic blood pressure between the arms, blood pressure will be measured at the non-dominant arm. Otherwise blood pressure will be measured at the arm with the higher blood pressure. The measurement will be done digitally using the instruments available at 1st Chair and Department of Cardiology.

### **5.2.4.2 Body temperature**

Body temperature will be measured at the forehead using digital thermometer available at 1st Chair and Department of Cardiology.

## **5.2.5 Other safety assessments**

Chest x-ray and echocardiography will be conducted as other safety assessments.

## **5.3 Other assessments**

### **5.3.1 Patient reported outcomes (PRO)**

PROs will be collected via paper forms and kept in the Investigator's Study File. The following measures will be collected as PRO:

- Symptoms (cardiovascular, respiratory, gastrointestinal, urogenital, neurological, musculoskeletal),
- Health-related quality of life (HRQL)

### 5.3.1.1 Name of PRO method or questionnaire

- State-of-the art used at 1st Chair and Department of Cardiology to assess symptoms.
- SF-12 Health Survey validated in patients after myocardial infarction to assess quality of life [17].

### 5.4 Pharmacokinetics

Not applicable

### 5.5 Pharmacodynamics

Not applicable.

### 5.6 Pharmacogenetics

Not applicable

### 5.7 Biomarker analysis

Concentrations of PEV and other biomarkers will be analysed in citrate-anticoagulated plasma prepared according to recently standardized protocols for handling and storage of human body fluids for analysis of extracellular vesicles [14,18]. Venous blood will be collected from fasting individuals to measure concentrations of EVs and platelet aggregation. The protocol for blood collection and handling is enclosed in Appendix D. Blood sampling will be conducted in all subjects three times: (i) 24 hours following administration of loading dose of clopidogrel, (ii) 48 hours following randomisation to ticagrelor or clopidogrel group, and (iii) 6 months following the index hospitalization. PEV analysis

- Concentrations of PEVs will be determined by state-of-the art flow cytometry (Apogee A60 Micro, UK) [14]. A selection of typical PEV samples will be isolated by size-exclusion chromatography [19] and analysed by transmission electron microscopy to confirm the presence of PEV and to study PEV morphology.
- Platelet function

Platelet function will be assessed by Multiplate impedance aggregometry (Multiplate Analyzer, Roche Diagnostics, Germany) using adenosine diphosphate (ADP; 6.5 µM) and thrombin receptor-activating peptide (TRAP, 32 µM) as agonists. Methodology applied to measure platelet function enables rapid and reliable on-site evaluation of platelet function,

including monitoring of platelet inhibition in patients treated with the P2Y12 receptor antagonists [20].

#### **5.7.1 Storage, re-use and destruction of biological samples**

All samples will be stored at 1st Chair and Department of Cardiology in a freezer, at the temperature of -80°C, under continuous temperature monitoring. In case of the freezer breakdown, the samples will be immediately transported to the nearby Centre for Preclinical Research and Technology (5 minutes walking distance). Only one freeze-thaw cycle will be permitted to analyse biomarkers. The re-use of thawed samples will not be permitted in course of the study. Every effort will be made to avoid destruction of stored samples.

#### **5.7.2 Labelling and shipment of biological samples**

All collected samples will be labelled with a unique code number prepared using Brady Label Printer (Brady, US) and analysed in one block by an operator blinded to patient- and treatment-related data. All samples will be transported on dry ice to Vesicle Observation Centre, Academic Medical Centre, University of Amsterdam, The Netherlands for analysis.

#### **5.7.3 Chain of custody of biological samples**

The PI or the study nurse will withdraw the blood with strict adherence to the protocol. The PI will prepare the plasma and transport the samples for storage (2 minutes walking distance). The PI will be the only person handling the samples to minimize the risk of sample handling variability, thereby maximizing the reliability of obtained results. The samples will be stored as described in the point 5.7.1. of the protocol until shipped to the Vesicle Observation Centre, Academic Medical Centre, University of Amsterdam for analysis.

#### **5.7.4 Withdrawal of Informed Consent for donated biological samples**

Subjects are free to withdraw the Informed Consent for donated biological samples at any time for any reason. The donated biological samples from subjects who withdrew a consent will be excluded from analysis.

## **6. SAFETY REPORTING AND MEDICAL MANAGEMENT**

### **6.1 Definition of adverse events**

Adverse events (AE) and serious adverse events (SAE) will be defined according to the guidelines of Food and Drug Association. AE will be defined as the development of an undesirable medical condition or the deterioration of a pre-existing medical condition occurring during the study in a subject administered a pharmaceutical product which does not necessarily has a causal relationship with the product. SAE will be defined as any AE which fulfil one or more of the following criteria:

- Results in death;
- Is immediately life-threatening;
- Requires hospitalization;
- Results in persistent or significant disability or incapacity.
- Is a congenital anomaly/ birth defect.

The following hospitalisations will not be considered to be SAE:

- Those planned before entry into the study;
- Elective treatment for a condition unrelated to study indication or study treatment;
- Occurred on an emergency outpatient basis and do not result in admission (unless fulfilling other criteria in SAE definition);
- Part of normal treatment or monitoring of the study indication and are not associated with any deterioration in condition.

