## **6.2 Reporting of serious adverse events**

Information about all SAE will be recorded on the SAE Form in Investigator's Study File. All events documented in the SAE Form will be reported within 24 hours to the Sponsor (personally or via fax) and to the Office of Medicinal Products, Medicinal Devices and Biological Products (via the online form available at [www.urpl.gov.pl](http://www.urpl.gov.pl)). All SAEs are to be submitted to the AstraZeneca Product Safety mailbox:

[[contact]](mailto:[contact])

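### The listed SAE criteria omit prolongation of an existing hospitalisation, so an index-stay event that is serious only because it delays discharge carries no SAE label and triggers no 24-hour report

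*Combined protocol and SAP*

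**What the plan says.** Section 6.1 (Definition of adverse events) first says that AEs and SAEs follow an outside guideline, which it names but does not reproduce. It then gives its own rule: "SAE will be defined as any AE which fulfil one or more of the following criteria". The five criteria are "Results in death", "Is immediately life-threatening", "Requires hospitalization", "Results in persistent or significant disability or incapacity", and congenital anomaly or birth defect. Four kinds of hospitalisation are then excluded. The fourth reads "Part of normal treatment or monitoring of the study indication and are not associated with any deterioration in condition".

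On timing, Section 6.1.1 says: "AE and SAE will be analyzed at each visit during index hospitalization and at the last visit at 6-months". On consequences, the section headed Reporting of serious adverse events says: "All events documented in the SAE Form will be reported within 24 hours to the Sponsor". It extends the same reporting to the national medicines authority and also sends SAEs to the manufacturer's safety mailbox.

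Events that are not SAEs still go on the AE Form (Recording of adverse events) and are reported descriptively by treatment group (Section 8.3.2).

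**The concern.** The hospitalisation criterion asks whether an event leads to hospital care. That works for a subject at home. It does not work cleanly for a subject already in hospital, and in this trial the first days on study treatment are spent in the index admission for myocardial infarction. An in-hospital complication that delays discharge has the same practical weight as one that leads to readmission, yet the list names only the second.

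The SAE label and the expedited report are at stake. The label feeds the safety objective in Section 2.3, where AEs and SAEs are an outcome to be described for ticagrelor relative to clopidogrel. The expedited report is how the Sponsor, the authority and the manufacturer learn of an event promptly. Both would be missing for this class of event in the days just after randomisation.

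**Working it through.** The plan states no figure on this point, so there is none to reproduce. The check is a reading of the sections together, with one count.

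**1. Where subjects are.** The schedule in Section 4 shows AE review on Days 0, 1, 3, 5 and 168, with randomisation at the Day 0 visit. The table's columns are imperfectly aligned in the text available, so this rests on the order of the entries. Section 6.1.1 places every AE review other than the 6-month one in the index hospitalisation. Hence 5 − 1 = 4 of the 5 reviews fall in that stay, and so does randomisation. The synopsis gives the ticagrelor load to subjects randomised to ticagrelor, so it follows randomisation and belongs to the same period. The clopidogrel load is different: Section 1.2 (Doses) allows it before hospital admission.

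**2. Apply the five criteria to an inpatient whose event delays discharge and does nothing worse.** A non-life-threatening bleed that holds the subject in hospital is an example.

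| Criterion in Section 6.1 | Met? |
|---|---|
| Death | No |
| Immediately life-threatening | No |
| Requires hospitalisation | Not on a plain reading: the subject was already admitted for another reason |
| Persistent or significant disability or incapacity | No |
| Congenital anomaly or birth defect | No |

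The documents contain no wording on prolonged stay and no criterion for medically important events that could catch it.

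**3. Apply the same criteria to the same event after discharge, leading to admission.** The hospitalisation criterion is met, so it is an SAE. The classification changes with the date, not with the event.

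**4. Follow the consequence.** The 24-hour report attaches to events on the SAE Form. The first event goes only on the AE Form, with its description, dates, CTCAE grade, causality, action taken and outcome (Section 6.1.3). The second goes on the SAE Form and is reported.

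**5. Check the form fields.** For SAEs, Section 6.1.3 asks for the reason the event is serious and the date of hospitalisation. For a stay-prolonging event, no listed reason fits, and the hospitalisation date would precede the event.

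**6. Size.** The number of affected subjects would be 60 × p, where p is the proportion with such an event. The documents give no value or range for p. The share of reviews (4 of 5) is not a substitute: Days 0 to 5 are 5/168 = 3.0% of the treatment period, so visits and time at risk give very different pictures.

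**The case against.** The strongest reply is that Section 6.1 does not stand alone. Its opening sentence adopts an outside guideline, and an investigator following that source might use a wider definition than the printed list. This stands as a limit on certainty: the documents do not show that stay-prolonging events would in practice go unreported. It does not remove the gap. The guideline's text is not in the protocol, it is not among the listed references, and staff completing the form will work from the five criteria. If the source is wider, the list departs from it and should be brought into line.

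A second reply is that the fourth exclusion covers only hospital care without deterioration, which implies that a complication needing further inpatient care could count as requiring hospitalisation. That is a possible reading. But an exclusion that does not apply is not a criterion that does, so the most it establishes is ambiguity.

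Third, little is lost. The event is still recorded and described by arm, the same rule applies to both arms, and Section 10.3 has the investigator inform the ethics committee of serious or unexpected events. This is right about the data. It does not restore the SAE label or the 24-hour report, and Section 10.3 sets no time limit.

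A reader might also infer that serious early events in general would escape SAE reporting. The documents do not support that: fatal, immediately life-threatening and disabling inpatient events remain SAEs. Nor can one say that all subjects are inpatients when loaded, because the clopidogrel load may precede admission.

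**Conclusion.** The point holds in a narrow form. The printed criteria leave out prolongation of an existing hospitalisation, in a trial where randomisation, the ticagrelor load and four of five AE reviews take place during an admission. The events affected are those whose only serious feature is a delayed discharge. For these, SAE status and the 24-hour report depend on whether the event falls before or after discharge.

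This rests on a plain reading of the hospitalisation criterion and on Section 6.1.1 for where the early visits take place. It does not rest on the content of the outside guideline, which cannot be seen. A reader may be tempted to attach a number of missed SAEs. Any such number would be an assumed rate multiplied by 60, with no support in the documents, so none is given.

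The primary endpoint, its analysis and the sample size are unaffected. The change is worth making because it concerns expedited safety reporting and costs almost nothing.

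**What to change.** - In Section 6.1, extend the criterion so that it reads "Requires hospitalization" followed by *or prolongs an existing hospitalization*.
- State that the fourth exclusion still applies to the index stay, so that ordinary care of the infarction without deterioration does not become an SAE.
- Check the whole list against the guideline that the section invokes, cite that guideline in the references, and resolve any difference.
- In Section 6.1.3 and on the SAE Form, add prolongation of hospitalisation as a reason for seriousness, and allow for an admission date earlier than the event.

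The cost is a short protocol and form change and a few more 24-hour reports. No analysis changes.
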